3 SUBJECT SELECTION

3.1 *Study Population*

Men with a histologically confirmed diagnosis of non-metastatic prostate adenocarcinoma, meeting the inclusion and exclusion criteria below, and electing to undergo definitive radiation treatment with SBRT, will be eligible for participation in this study.

3.2 *Inclusion Criteria*

1. Biopsy-proven diagnosis of prostate adenocarcinoma
2. NCCN defined low-, intermediate- and high-risk prostate cancer
3. Age ≥ 18
4. Patient must have prostate MRI with a PIRADS 3-5 lesion *or* PSMA PET with an avid intraprostatic lesion

3.3 *Exclusion Criteria*

1. History of prior pelvic radiation (external beam or brachytherapy)
2. Inability to undergo MRI
3. Patients with metastatic disease (other than pelvic lymph nodes) are ineligible for this study
4. AUA score >17

4 REGISTRATION PROCEDURES

4.1 *Patient Registration*

Before any protocol specific procedures can be carried out, investigators/staff will fully explain the details of the protocol, the study procedures and the aspects of patient privacy regarding research information. Patients will be provided a comprehensive explanation of the proposed treatment including the type of therapy, the rationale for treatment on the protocol, alternative treatments that are available, any known adverse events, the investigational nature of the study and the potential risks and benefits of the treatment. The informed consent document will meet all requirements of the Institutional Review Board (IRB). All subjects/patients are informed in the consent that participation or refusal to participate in the research study will not affect any of the clinical treatment or services to which they would otherwise be entitled.

The physicians who may obtain informed consent are listed on the title page of this protocol. The informed consent form will be signed by the participant and the registering physician. Once signed, a copy will be given to the patient and one will be maintained with the patient's medical record. Once eligibility is confirmed and informed consent is documented, the patient will be registered by the study coordinator/data manager.

Patients will be centrally registered with the Office of Billing Compliance. To register a patient, submit the following documents via the JIRA Registration Process:

- Legible copy of the HRBAF
- Signed informed consent

Registration must be completed within 24 hours of the signing of informed consent.

5 STUDY PROCEDURES

| | Pre-Study | Fx 1 | Fx2 | Fx 3 | Fx 4 | Fx 5* | Post-RT Visit (3-6 month s/p RT) |
|--|-----------|------|-----|------|------|-------|----------------------------------|
| Informed consent | X | | | | | | |
| Demographics | X | | | | | | |
| PSA | X | | | | | | X |
| Acute/Late Toxicity Assessment (CTCAE) | X | | | | | X | X |
| EPIC-26, AUA | X | | | | | | X |
| Imaging: Planning CT/MR; | X | | | | | | |
| Optional: blood draw and microbiome sample | X | | | | | X | X |

**at physician's discretion, lymph nodes may be targeted in the radiation field, either in 5 fractions or over 5-6 weeks using standard fractionation*

5.1 Pre-Study Visit

At the initial screening visit, patient will undergo:

- Informed consent
- Medical history
- Baseline EPIC-26 Questionnaire, AUA

5.2 Imaging Studies

Patients enrolling on the protocol will be treated as follows. Placement of a rectal spacer is optional; patients who refuse or decline a rectal spacer will have the option to be treated with an endorectal balloon (ERB). Patients will be instructed to undergo a Fleet enema prior to planning CT and prior to each SBRT treatment.

All patients will be sent for a pelvic MRI for treatment planning purposes, or have an MR on the Viewray machine. This should ideally be done within 1-2 weeks of the treatment planning CT. The ideal MRI, if not done on the Viewray, will be 3Tesla and in a position similar to treatment position, without use of an endorectal coil which can distort the prostate shape. If rectal spacer is

placed, the treatment planning MRI should be performed after the spacer placement.

Treatment planning CT will be performed with vac loc immobilization. Patients will be advised to drink 1-2 cups of water 1 hour prior to the CT simulation to allow for a comfortably full bladder, if tolerated. A rectal catheter will be utilized to dispel any excess bowel gas, if necessary. A urethral catheter to delineate the urethra at time of simulation can be considered if it is difficult to visualize the urethra on initial MRI. Oral contrast may be administered as per standard protocol if lymph nodes are being targeted.

5.3 Radiation Treatment Planning

5.3.1 Contours

The treatment planning CT will be fused to the T2 sequence of the planning MRI. The prostate +/- seminal vesicles (SV) +/- pelvic lymph nodes will be contoured as the clinical target volume (CTV) as per usual practice. **Select PIRADS 3-5 and/or PSMA avid (if PSMA PET/MR is available) and/or biopsy positive nodules (chosen based on physician's clinical judgment and correlation with biopsy findings)** will be contoured as gross tumor volume(s) (GTV). There will be no planning target volume (PTV) expansion for the GTV. The PTV expansion for the CTV will be 0-5 mm on the prostate, depending on physician discretion as per standard care.

The rectum will be drawn from the bottom of the ischial tuberosities to the sigmoid flexure. The urethra will be delineated on MRI from the prostatic apex, to entry of urethra into the penile bulb, using a 5 mm brush. The physician will have the option of placing a urethral catheter at time of sim as per standard care.

The bladder, femoral heads, penile bulb will also be contoured as normal structures.

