Hypothesis: MRI-guided treatment planning and delivery can **selectively target high-risk prostate nodules and deliver a higher radiation dose, to achieve maximal local control without increasing treatment toxicity**

Primary objective: **To assess feasibility and safety of delivering MRI-guided prostate SBRT with a simultaneous integrated boost to MRI-visible lesions.**

[figure not shown]
Feasibility is defined as a plan meeting treatment planning objectives and normal tissue constraints. Specifically the dose distribution of the MRI-guided technique, will be assessed with regard to fulfilling protocol requirements of: a) coverage of the planning target volume (PTV) , b) constraints to organs at risk (OAR) by dose volume histogram (DVH) analysis and whether this can be done through standard set-up techniques or non-invasively through MRI based planning, c) coverage of high-risk prostate nodules. The total dose (either 37.5, 40, 42.5 or 45 Gy) will be determined by selecting the plan that delivers the highest dose to contoured visible nodules while maintaining normal tissue constraints to the urethra and rectum. We will track the number of treatment plans for each dose level (37.5, 40, 42.5 or 45 Gy) that can be delivered while meeting radiation planning objectives.

Safety of this approach will be determined by assessing acute GI/GU toxicity (CTCAE 4.0 criteria). Treatment will be deemed safe if there is no acute >G3 GI/GU toxicity within the first 30 days of treatment (CTCAE 4.0 criteria). Given that the treatment plans will meet rigorous normal tissue constraints used for standard prostate SBRT, we do not anticipate any increased toxicity on this study compared to standard prostate SBRT.

Secondary objectives:

1. To obtain health-related quality of life (HRQOL) measured using: 1) the Expanded Prostate Cancer Index Composite (EPIC) short form questionnaire, 2) AUA. Assessment will occur at baseline, and at first follow up.

SCHEMA

Blood samples for immune monitoring studies and stool samples for microbiome studies will be collected at baseline, end of Radiation at 3-6 months post follow up visit.

TABLE OF CONTENTS

| | |
|--|-----------|
| PROTOCOL SUMMARY | 9 |
| SCHEMA..... | 11 |
| 1 STUDY OBJECTIVES | 14 |
| 1.1 PRIMARY OBJECTIVES | 14 |
| 1.2 SECONDARY OBJECTIVES | 14 |
| 2 BACKGROUND | 14 |
| 2.1 PROSTATE CANCER RADIOTHERAPY..... | 14 |
| 2.2 BIOLOGICAL RATIONALE FOR SBRT | 15 |
| 2.3 SBRT OUTCOMES..... | 16 |

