1.1 Primary Objectives

1.1.1 Determine the feasibility and safety of delivering SBRT w/SIB without increased acute G3 GI/GU toxicity.

Feasibility is defined as a plan meeting treatment planning objectives and normal tissue constraints. Specifically the dose distribution of the MRI-guided technique, will be assessed with regard to fulfilling protocol requirements of: a) coverage of the planning target volume (PTV) , b) constraints to organs at risk (OAR) by dose volume histogram (DVH) analysis and whether this can be done through standard set-up techniques or non-invasively through MRI based planning, c) coverage of high-risk prostate nodules. The total dose delivered (either 37.5, 40, 42.5 or 45 Gy mean dose to the contoured nodule) will be determined by selecting the plan with the highest dose to visible nodules while maintaining normal tissue constraints to the urethra and rectum. We will track the number of treatment plans for each dose level (37.5, 40, 42.5 or 45 Gy) that can be delivered while planning objectives.

Safety of this approach will be determined by assessing acute GI/GU toxicity (CTCAE 4.0 criteria). Treatment will be deemed safe if there is no acute >G3 GI/GU toxicity within the first 30 days of treatment (CTCAE 4.0 criteria). Given that the treatment plans will meet standard normal tissue constraints used for prostate SBRT, we do not anticipate any increased toxicity on this study compared to standard prostate SBRT.

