2.2 Biological rationale for SBRT

Proponents of prostate cancer hypofractionation argue that the rectum and bladder are less sensitive to increases in dose per fraction than prostate cancer and that therefore hypofractionation should yield negligible increases in late toxicity while providing improved cancer control. The α/β is a theoretical measure of a tissue's predicted response to a dose of radiation, relative to the size of the dose delivered per fraction. Conventional daily doses of radiation are based on the presumed high α/β ratios of most malignant tumors. Higher α/β ratios mean that tumor response is less dependent on the amount of radiation administered with each fraction when compared to adjacent normal tissue, and therefore that a lower radiation dose per treatment can typically be used. Lower tumor α/β ratios mean that a larger dose of radiation per treatment can provide improved efficacy in terms of therapeutic ratio, tumor control versus risk of complications. A large body of work theorizes that the α/β for prostate cancer is low (~1.5), implying that a hypofractionated schedule could improve prostate cancer control, while maintaining a low risk of severe normal tissue

complications (see Table 1).⁷ The radiobiological linear-quadratic cell survival model was used to calculate the biologically equivalent doses for tumor control and complications to normal organs, using standard 2 Gy fractions delivered five times a week.⁸⁻¹⁰

Table 1. Equivalent total doses in 2 Gy per fraction (EQD2) based on α/β Biologically Effective Doses (BED)

| | α/β (Gy) | EQD2 Standard (1.8 Gy x 45 fx) | EQD2 SBRT (7 Gy x 5 fx) | EQD2 SBRT (7.5 Gy x 5 fx) | EQD2 SBRT (8 Gy x 5 fx) | EQD2 SBRT (8.5 Gy x 5 fx) | EQD2 SBRT (9 Gy x 5 fx) |
|------------------------|---------------------|--------------------------------------|----------------------------|------------------------------|----------------------------|------------------------------|----------------------------|
| Total Dose (Gy) | | 81 | 35 | 37.5 | 40 | 42.5 | 45 |
| Tumor | 1.5 | 76.37 Gy | 85 Gy | 97.65 Gy | 110 Gy | 123.07 Gy | 135 Gy |
| Fibrosis/stricture | 2 | 76.95 Gy | 78.75 Gy | 89.06 Gy | 100 Gy | 111.56 Gy | 123.7 Gy |
| Telangiectasia | 4 | 78.3 Gy | 64.17 Gy | 71.88 Gy | 80 Gy | 88.54 Gy | 97.5 Gy |
| Rectum | 4 | 78.3 Gy | 64.17 Gy | 71.88 Gy | 80 Gy | 88.54 Gy | 97.5 Gy |
| Bladder | 4 | 78.3 Gy | 64.17 Gy | 71.88 Gy | 80 Gy | 88.54 Gy | 97.5 Gy |

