2.3 SBRT Outcomes

To date, results from prospective and retrospective studies demonstrate good biochemical control and low toxicity for SBRT, with commonly used doses ranging from 35-45 Gy in 5 fractions (see Table 2). SBRT compares favorably to outcomes for standard fractionation EBRT to 81 Gy, which has 10-year biochemical RFS of 91%, 78% and 62%, respectively, for low-, intermediate- and high-risk prostate cancer, and late Grade 3 gastrointestinal (GI) and genitourinary toxicity of 1% and 5%, respectively.¹¹ There is a lack of consensus regarding the appropriate dose to use for prostate SBRT. Extrapolating from dose escalation studies in conventionally fractionated EBRT,^{12,13} a higher dose in SBRT is hypothesized to result in improved local control. However, delivery of higher dose results in small but significant increase in GU toxicity. Katz and Kang showed significantly higher late grade 2-3 GU toxicity with 36.25 Gy compared to 35 Gy (13.2 vs 8.8%, P<0.05). With 35 Gy in five fractions, the majority of toxicity was grade 2, and overall toxicity was low without impacting GU quality of life. As shown in Table 2, late grade 3 GU/GI toxicity after SBRT appears to be comparable to that of conventionally fractionated EBRT, ranging from 0.6 – 3%^{4,6} with longest median follow-up of 7 years.

Table 2. Biochemical control after prostate SBRT. *prospective

| Study | SBRT Dose (5 fx) | FU | # Pts | Risk Categories | bPFS | Toxicity ≥ 3 |
|-------------------------|---------------------|-----|-------|----------------------------------|----------|-------------------|
| Bolzicco ^{14*} | 35 Gy | 36m | 71 | Low (41%), Int (42%), High (17%) | 3y 94.4% | GI 0%, GU 1% |
| King ^{15*} | 35-36.25 Gy | 5y | 41 | Low, Favorable Int Risk | 5y 92.7% | GI 0%, GU 3.5% |

| | | | | | | |
|-----------------------------------|---------------|--------|-----|---------------------------------|--|------------------|
| McBride 16* | 36.25-37.5 Gy | 44.5 m | 45 | Low | 3y 97.7% | GI 4.4%, GU 2.2% |
| Madsen ¹ 7* | 33.5 Gy | 41m | 40 | Low | 4y 90% | GI 0%, GU 0% |
| Fuller ¹⁸ * | 38 Gy/ 4 fx | 60m | 259 | Low (43%), Int (57%) | 5y Low 100%, Int 88.5% | GI 0%, GU 3.1% |
| Kim ¹⁹ | 45-50 Gy | 42m | 47 | Low (38%), Int (62%) | 4y 98% | GI 0%, GU 0% |
| Loblaw ² 0* | 35 Gy | 55m | 84 | Low | 5y 98% | GI 1%, GU 1% |
| Mantz ²¹ * | 40 Gy | 60m | 102 | Low, Fav Int | 5y 100% | GI 0%, GU 0% |

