2.6 ViewRay: a unique radiation delivery approach

The ViewRay MRIdian Linac system is a radiation delivery machine that integrates a linear accelerator with real-time MRI imaging. The ViewRay machine allows fusion of MR imaging with treatment planning. The uniqueness of this approach is the image guided delivery component, based on precise MRI-based detection of target and normal tissue during treatment in real-time. The ViewRay will provide real-time MRI imaging to ensure that the high-dose region is precisely targeted. MRI guided radiation has the benefit of not requiring fiducial implantation or excess radiation exposure from multiple cone beam CT. Furthermore, motion monitoring can be

performed with images acquired up to 4 frames a second, allowing live feedback of treatment position.

ViewRay offers the ideal system for delivery of prostate SBRT, due to its ability to provide image guidance “live”, during treatment. Real-time MRI imaging allows superior soft-tissue differentiation with excellent visualization of the prostate. This ViewRay platform offers the ideal setting for this study, that aims at precisely delivering prostate SBRT with a simultaneous integrated boost to visible nodules.

The goal of this study is to assess feasibility and safety of using the ViewRay to deliver prostate SBRT with SIB. Feasibility is defined as the ability to deliver treatment as planned (within the constraints defined in Section 5.3 Radiation Planning) and safety is defined as lack of acute G3 GI or GU toxicity within 30 days. The proposed SBRT dose (35-36.25 Gy in 5 fractions to the whole prostate) has been reported in the literature to be safe and well tolerated (Table 2), with no acute G3 toxicity. The proposed boost dose of an additional 0.5, 1.0, 1.5 or 2 Gy per fraction (total dose 37.5-45 Gy, depending on normal tissue constraints) is within the range of current standard of care SBRT doses, and is expected to be well-tolerated if normal tissue constraints are met. By applying rigorous normal tissue constraints and capitalizing on the imaging capability of the ViewRay we plan to deliver a treatment that is non-invasive and exceptionally precise.

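### The urethral contour in 5.3.1 stops at the prostatic apex, so the urethral limit that helps select the boost level does not cover the urethra inside the prostate

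*Combined protocol and SAP*

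**What the plan says.** Section 5.3.1 gives each structure a drawing rule. For the urethra the rule is MRI delineation with a 5 mm brush, running "from the prostatic apex, to entry of urethra into the penile bulb". The same section allows a catheter at simulation, and 5.2 says "A urethral catheter to delineate the urethra at time of simulation can be considered" when the urethra is hard to see on the first MRI.

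Section 5.3.2 sets the urethral maximum at 40 Gy and tolerates up to 42 Gy. It also sets the boost: a mean nodule dose of 37.5, 40, 42.5 or 45 Gy, choosing the highest level that respects the rectal and urethral limits. The Protocol Summary states the same rule: the chosen plan is the one that "delivers the highest dose to contoured visible nodules while maintaining normal tissue constraints to the urethra and rectum". Section 1.1 repeats it ("while maintaining normal tissue constraints to the urethra and rectum") and adds a tally: "We will track the number of treatment plans for each dose level".

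Sections 10 and 12.1.1 make compliance with the organ limits of 5.3 the second of three feasibility criteria, (b). Section 12.4 plans subgroup summaries of feasibility, safety and both combined within each of the four dose levels.

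**The concern.** A urethral limit that chooses the boost for nodules inside the prostate has to be measured on the urethra inside the prostate. The written contour begins where that segment ends. Taken literally, one of the two named selection constraints would restrain the boost little, except for nodules close to the apex.

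Two things are at stake. The first is patient protection: 2.6 says the boost "is expected to be well-tolerated if normal tissue constraints are met", and that condition is weaker than it looks if the constrained structure is the wrong segment. The second is what the results mean: the level a plan receives, the tally by level, the subgroups by level and criterion (b) all depend on which structure is scored.

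**Working it through.** This is a check of text against text. There is no planned figure to reproduce.

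1. **Extent of the structure (5.3.1).** The upper end is the prostatic apex and the lower end is the penile bulb. The apex is the bottom of the gland and the bulb lies below it, so the in-gland urethra is outside both end points. The contoured segment lies outside the prostate CTV and at most partly inside the 0-5 mm PTV margin.

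2. **Any other extent?** None was found. The catheter wording in 5.2 and 5.3.1 helps to see the urethra but names no segment. The limit in 5.3.2 says only urethra. The references in 5.3.1 to usual practice and standard care attach to the CTV, the PTV margin and the catheter option, not to the length of the urethra.

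3. **What the limit is used for.** The Protocol Summary, 1.1 and 5.3.2 all use it, with the rectal limit, to choose the nodule dose. The nodules are inside the prostate, and 5.3.1 gives them no PTV expansion.

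4. **Could the limit bind inside the gland?** Inputs from 5.3.2:
   - Whole-gland prescription: 5 × 7 = 35 Gy to 5 × 7.25 = 36.25 Gy, below 40 Gy.
   - Boost means against the 40 Gy limit: 37.5 − 40 = −2.5; 40 − 40 = 0; 42.5 − 40 = +2.5; 45 − 40 = +5 Gy.
   - Boost means against the 42 Gy tolerance: −4.5, −2, +0.5 and +3 Gy.

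   The boost levels straddle the limit, so a limit on the in-gland urethra could decide the level for a nearby nodule. These differences are not estimates of urethral overdose, because a nodule mean is not a urethral maximum. Nor do they mark off the affected levels. Section 5.3.2 sets no maximum dose within the nodule, so a nodule with a 40 Gy mean can contain points above 42 Gy, while a 45 Gy nodule far from the urethra may raise no issue.

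5. **Do other limits close the gap?** Section 5.3.2 also limits rectum, bladder, penile bulb, femoral heads and small bowel. The rectal and bladder limits restrain many plans, but neither directly caps dose to in-gland urethra away from those organs. No maximum is set for the prostate or the PTV.

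6. **Route into the results.** A level chosen on the written contour enters the tally (1.1) and the subgroups (12.4), and the plan is scored as passing (b). Because 37.5 Gy remains as a fallback, scoring the whole urethra would more often lower a plan's level than make it infeasible. The effect therefore falls mainly on the breakdown by level rather than on the pooled feasibility percentage.

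**The case against.** The strongest reply is that nobody would plan this way. The limit exists to cap an intraprostatic boost, the Protocol Summary and 1.1 appeal to the normal tissue constraints used for prostate SBRT, physicians draw the contours, and a literal reader would be applying a boost constraint where it hardly constrains. Nothing shows that any plan was made on the literal contour. This stands as a limit on the consequence: the effect is conditional. It does not make the rule right. The text gives explicit end points, and if some planners follow them and others do not, dose level and criterion (b) are scored on different structures across patients.

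A second reply is that the size is unknown and the pooled endpoints are robust: the rectal and bladder limits still apply, toxicity is graded clinically, and the analysis is descriptive, in 30 patients. This also stands.

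Three stronger readings are tempting and not supported:
- A reader might infer a specific excess of 0.5 or 3 Gy at the top two levels, or a biological dose increase from Table 1. That requires a urethral point to receive the nodule mean, which nothing in the documents supports.
- A reader might infer that only 42.5 and 45 Gy are affected. Step 4 of the working shows why that is unsafe.
- A reader might infer a toxicity increase from 2.3, which says "delivery of higher dose results in small but significant increase in GU toxicity" (late grade 2-3 GU toxicity 13.2% at 36.25 Gy against 8.8% at 35 Gy). Those are different prescribed doses to the whole gland, not focal urethral doses, so this is indirect support at most. The primary safety endpoint covers 30 days, but CTCAE assessment is also scheduled at 3-6 months.

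Finally, no second section states a conflicting extent. The conflict is between the contour's end points and the use made of the limit.

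**Conclusion.** The point holds. As written, 5.3.1 excludes the in-gland urethra from the structure on which the 40/42 Gy limit is scored, and that limit helps select the boost level and forms part of criterion (b). A boost that overdoses the in-gland urethra could therefore be selected and counted as compliant.

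That the end points are a drafting error is an inference from how the limit is used; the documents do not state the intent. The effect arises only where the end points are followed literally. The number of plans affected and the size of any excess dose cannot be derived. The expected effect on the pooled primary results is limited. The correction should still be made, because the text governs a patient-protection limit and the meaning of the dose-level breakdown.

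**What to change.** Amend 5.3.1 so that the urethra is contoured through the whole prostate: from the bladder neck, through the apex, to the penile bulb. The bladder neck is a proposed upper end, since the documents name none; what matters is that the full in-gland segment is included. State that the 40/42 Gy limit, the choice of boost level and feasibility criterion (b) are scored on that structure for all plans from then on.

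If any patients were already planned on the literal contour, leave their delivered dose level and primary feasibility result as they are. Re-read their urethral DVH on the corrected contour and report it as a labelled sensitivity analysis of criterion (b).

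The cost is one or two sentences, plus a DVH re-read for those patients, if there are any. The downside is that some future plans may drop a dose level. If planners already contour the whole urethra, no plan changes and the text simply matches practice.
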